Understanding the impact on QoL, particularly on physical, mental, and social health, for these three bladder management methods and the impact of urinary-specific complications using patient reported outcomes is of particular interest for patients, caregivers, and clinicians. These factors are important for comprehensive QoL assessment among patients with neurogenic bladder and SCI as identified in previous studies and by our patient partners and stakeholders.

This is a longitudinal observational study for three different bladder management strategies for an estimated 1,500 neurogenic bladder and SCI patients. Patients will be identified and recruited at the (1) University of Utah, (2) University of Minnesota, and (3) University of Michigan (4) University of Western Ontario. To be eligible, a patient must have a spinal cord injury or neurogenic bladder with urinary issues and be using one of the three bladder management treatments (CIC, IDC or urinary reconstruction). We plan to use the Neuro-QoL developed for PROMIS, a computerized adaptive test questionnaire to assess overall OoL and the Neurogenic Bladder Symptom Score (NBSS) to capture the impact of urinary specific issues and complications on QoL. The primary and secondary aims of this study are to compare total Neuro-QoL score and total NBSS score, respectively, across the three common bladder treatments. We will also compare scores for the sub-domains of these surveys, which include physical, mental and social function for the Neuro-QoL, and Incontinence, Storage and Voiding Symptoms, Complications, and a QoL item for the NBSS. Additionally, we will determine whether complication rates for one of the three methods impact Neuro-QoL scores.

REFERENCES

1. de Seze M, Ruffion A, Denys P, Joseph PA, Perrouin-Verbe B. The neurogenic bladder in multiple sclerosis: review of the literature and proposal of management guidelines. Multiple sclerosis (Houndmills, Basingstoke, England). 2007;13(7):915-28.

6. Able to provide informed consent and authorization that the participant has been informed of all pertinent aspects of the study prior to enrollment.

Exclusion Criteria:

Patients will be excluded that do not have neurogenic bladder, belong to a vulnerable population (pregnant, prisoners, mentally handicapped, etc..), or are less than 18 years of age.

Design

Survey/Questionnaire Research Observational Research

Study Procedures

Recruitment/Participant Identification Process:

1. Participants will be recruited during clinical visits for the Division of Urology. Participants with neurogenic bladder and or spinal cord injury will be asked in clinic if they would like to participate in the study. They will be provided with information about the study. If they agree to participate a study coordinator will obtain consent and authorization and then enroll them in the study.

2. Participants will be referred from the Rehabilitation Clinic and Physical Medicine and other clinics where spinal cord injury patients are treated. In cases such as these, we will go to the respective clinic and consent the participant if possible while they are at their clinic visits.

3. We will have a study website: nbrg.org where participants can click on a link for further information about the study and also be able to take a brief survey which will determine eligibility and then also have the ability to remote consent if they desire.

4. We will also have a Facebook ad that will link to the study's website. The Facebook ad will be constructed by the University of Utah's Marketing Department.

4. Public events where spinal cord injury patients attend will also be a possible recruitment entity where we would provide information to interested participants.

Informed Consent:

Description of location(s) where consent will be obtained:

Urology Clinic Physical Medicine and Rehabilitation Clinic Other University of Utah Health Care Clinics that involved potential participants At the study website Over the phone At public events where spinal cord injury patients would be in attendance

Description of the consent process(es), including the timing of consent:

Patients will be asked if they would like to participate in the study. If they agree than they will be given a consent and allowed to fully review the consent. The consent will specify when they will be contacted and how they will be contacted during the course of the study. When patients feel they have had enough time to fully review the consent they will be enrolled in the study. This process will be the same for patients consenting over the phone, except that patients will be either emailed or mailed a copy of the consent prior to the review of the consent. For patients that are remote consenting, the consent will be on the study website.

Procedures:

This study is an observational/questionnaire study. Patients will be identified and recruited at the (1) University of Utah, (2) University of Minnesota, (3) University of Michigan and (4) University of Western Ontario, Canada. To be eligible, a patient must have a spinal cord injury and/or neurogenic bladder with urinary issues and be using one of the three bladder management treatments (CIC, IDC or urinary diversion). We plan to use the Neuro-QoL developed for PROMIS, a computerized adaptive test questionnaire to assess overall QoL and the Neurogenic Bladder Symptom Score (NBSS) to capture the impact of urinary specific issues and complications on QoL.

Protocol Summary (ERICA) Page **8** of **13** IRB_00082971 IRB Approval 8/26/2015 Baseline Visit: Patients at this visit will be approached regarding study participation. After providing consent and authorization, the patient will have about a 30 minute interview, with a clinician like a physician, nurse, or physician assistant, or a study coordinator who will obtain the medical history. We will gather the following information for our study: patient name, MRN, address, telephone, and email address. If the patient provides consent over the phone or remotely at our study website, the 30 minute interview will take place over the phone.

The patient will be asked very routine questions about his/her health, medication usage, surgical history, physical exam findings, and specifics related to bladder management, bladder health, and specifics regarding the treatments previously received for treatment of neurogenic bladder.

At the end of this 30 minutes, if the participant would like to complete the first set of questionnaires while he/she is in clinic, he/she will answer the questions on a tablet (or paper if the patient prefers) about his/her quality of life, pain and bladder management. These questionnaires should take about 10 minutes to complete. If the participant does not have the time at the current clinic visit to complete these questions, a link will be emailed to the participant, which when clicked, will take the participant to the Assessment Center, where the questionnaires will be completed. For participants who don't have a computer, who are not able to use a computer or prefer to have the questions read to them, study personnel will set up a time to call and the questions will be completed over the phone.

The patient will be asked to complete the same questionnaires that were completed at baseline, every 3 months for up to 1 year. This will be accomplished by either 1) sending the participant the questionnaire link via email 2) calling the participant and completing the questionnaire via phone 3) approaching the participant at his/her next standard of care clinic visit (if this visit falls within the 3 month window) to see if he/she would like to complete the next set of questionnaires either by paper or table. Also, there is an Exit Interview that will be given when the participant finishes the study. This Exit Interview can be sent to the participant via email with a link to the questions, or the participant can do the Exit Interview over the phone with study personnel; whichever method the participant prefers. The Exit Interview asks questions about any changes over the past year in bladder management, any surgeries that might have affected bladder management and any complications that resulted in a change of bladder management for the participants. The Exit Interview questions will take approximately 15 to 20 minutes to complete.

Data from participants that meet the study criteria and are enrolled in the study will be collected for research purposes only. A participant list will be placed on an excel spread sheet that will be stored in a secure folder on a secure drive. Access to this secure folder is only granted by the IT department upon request by the Research Manager. The excel database will contain the following information: Patient full name, medical record number, phone number, email, where consent was obtained, date of consent, date the questionnaires were sent, date questionnaires were completed and target date of future questionnaires. Data from the baseline assessment will be stored in REDCap and will include the participant's full name, address, phone number, medical record number, date of birth, email address, date of injury, previous medical history information, and current medical history information.

For the questionnaires done at baseline and then again every 3 months, the participants are sent a link, which is generated upon study enrollment with a unique participant identification number and is specific to each individual participant. The questionnaire link is sent to the participant via email, which takes them to the Assessment Center where the questionnaires are completed. Some participants will have difficulty completing these questionnaires themselves either because they don't have access to a computer or because of physical limitations. For these participants, study personnel will call them and read the questions to them over the phone.

can only be assessed via the link that is sent to the participants, and no PHI is collected for the questionnaires at the Assessment Center. The participants are identified by their unique study ID only.

Termination of the project is contingent upon data analysis and manuscript preparation which should be completed in six years.

The University of Utah IRB will review this protocol and any modifications.

Procedures performed for research purposes only:

Statistical Methods, Data Analysis and Interpretation

The primary and secondary aims of this study are to compare total Neuro-QoL score and total NBSS score, respectively, across three common bladder treatments: CIC vs. IDC vs. Urinary diversion/bladder augmentation. While the total scores are our primary outcomes, we will also compare scores for the subdomains of these surveys, which include physical, mental and social function for the Neuro-QoL, and Incontinence, Storage and Voiding Symptoms, Complications, and a QoL item for the NBSS. We will also plan to report subgroup summaries to provide details specific to time since injury and/or treatment duration. The tertiary aim is to investigate whether the relationship between complication rate an effect modifier of the relationship between treatment groups (i.e. is complication rate an effect modifier of the relationship between treatment group and Neuro-QoL). For this aim we will also describe and compare complication rates across bladder treatment groups.

Analysis Plan Overview:

The benefit of this longitudinal design is that it will allow us to capture QoL and complications data on a large cohort for a fairly rare condition. Furthermore, the subjects captured with this design resemble a typical patient population, where subjects present at various times since injury and with varying treatment durations. This is a typical patient population encountered in clinical practice, where the goal is to appropriately council these patients on their treatment options. Because treatment history, outcomes, and covariates are recorded only for a 12-month period and are not available prior to the baseline assessment, it is not possible under our proposed design to evaluate the causal effects of the patients' full bladder treatment histories. Rather, we will characterize the association of the QoL score and other outcomes with the patient's bladder management treatment at enrollment (CIC, IDC or urinary diversion/bladder augmentation) during the 12-month follow-up period for each patient, with adjustment for demographic factors and injury characteristics. Thus the goal for

our primary analysis for aims 1-3 is to summarize patient experiences over the 12month period, defined by his/her treatment at enrollment (i.e., ignoring any changes in treatment). A secondary analysis for aims 1-3 will be to allow treatment group to be time varying for the 10-15% who are expected to change treatment during the course of the study. This latter type of analysis provides a more general characterization of QoL by treatment type, but it is limited in that it is more difficult to adjust for covariates -- more details are provided below.

Primary Analysis for Aims 1-2:

Our primary endpoints for aims 1 and 2 are the average of total QoL scores over time (total Neuro-QoL score and total NBSS score, respectively). For our primary analysis, these outcomes will be analyzed in a linear mixed effects regression framework, and our primary predictor variable will be the patient's baseline treatment type. Thus, even if a patient switches treatment during our study, we will ignore this change here and consider any change in OoL to just be part of a patient's typical one year experience starting from treatment X. Given that there are only five time points, it should be feasible to model within patient correlations using an unstructured covariance matrix. In these models we will evaluate the three possible pair-wise contrasts: CIC vs. IDC, CIC vs. Surgery and IDC vs. Surgery for statistical significance at the 0.017 Bonferroni-adjusted significance level. Key covariates that will be included in the aim 1-2 models are: time since injury at baseline (coded as a categorical variable with levels <1 year, 1-5 years, and >5 years), physical limitations severity (mild, moderate severe), time on bladder management strategy recorded at baseline (<6 months, 6m-1.5 years, >1.5 years), age at baseline (coded as <20, 20-30, 30-40, 40-50, >50), sex, follow-up time point and BMI. In addition, we hypothesize that interaction effects exist between treatment group at baseline and time on baseline treatment, time since injury, injury severity and patient age. This is because different treatments may have different complication rates, and longer times on a particular treatment may differ from shorter times on the treatment in terms of QoL. Similarly, patient satisfaction (and thus potentially QoL) with treatment type may vary with patient age, time since injury and injury severity. The possibility of additional pair wise interactions between treatment group and the covariates will be investigated in an exploratory fashion. Stata v.12 software will be used to extract the marginal coefficients, 95% confidence intervals (CIs) and p-values for each treatment group contrast in the presence of these interactions using the "margins" command (http://www.stata.com/stata11/margins.html). To summarize patient outcomes by treatment group, we will provide average QoL estimates and 95% CIs for some combinations of treatment group, treatment duration, time since injury, injury severity and age subcategories. While this corresponds to $3^{5}=243$ possible different subcategory combinations, these descriptive results will be estimated from our model based on the full available sample size. Thus these results will provide a profile of expected outcomes for each treatment group given different combinations of patient and injury characteristics.

Secondary and Additional Analyses for Aims 1-2:

As a secondary analysis, we will allow treatment group to be a time-varying predictor given that patients can change treatment during the course of the study. This analysis will characterize the average relationship between treatment type and QoL. The key covariates will be the same as for the main analysis, except that we will not consider the interaction between treatment group and time on treatment at baseline, since it is no longer sensible in the context of a changing treatment group (given that time on treatment at baseline corresponds to one particular treatment).

It is also interesting to study patients who switch treatments during the 12m follow-up period. We will investigate potential predictors of switching treatment groups in an exploratory fashion, by modeling treatment change (yes/no) as an outcome and baseline treatment group as a main predictor. This will allow us to evaluate whether the rates of change during the 12 month follow-up period vary by baseline treatment group. Other potential predictors of treatment change will include time on baseline treatment, time since injury, injury severity, patient age, sex and BMI.

Finally, we will repeat the primary analysis model for each of the subscales of the two surveys (using treatment type at baseline as a primary predictor). For the subscale analyses we will plan to report the marginal coefficients, 95% confidence intervals CIs and p-values for each treatment group contrast (3 pair-wise comparisons), and statistical significance will be evaluated at the 0.017 level.

Analysis Plan for Aim 3

For our tertiary aim of evaluating cumulative complication rates (categorized as 0, 1-3, 3-5, >5) by treatment group on QoL, we will adopt a similar modeling framework as described for Aims 1-2, except that complications will be included in the model along with its interaction with treatment group. We will use a likelihood ratio test to evaluate the statistical significance of this interaction term, i.e. to answer our main question of whether or not the relationship between cumulative complications and QoL differs by treatment group. We will also provide average QoL estimates and 95% CIs for combinations of subcategories of complications, treatment group, treatment duration, time since injury, and age using Stata's margins command. We will also plan to implement the Aims 1-2 secondary analysis where treatment group is modeled as a time varying predictor. Again these models will include the additional interaction term between treatment group and cumulative complications.

While our original analysis for our PCORI grant funding specified data collection for 12 months follow-up, any additional longitudinal data follow-up would be useful and novel data for the field and will be collected as available.

A Note on Missing Data

One benefit of the mixed effects modeling framework is that our models will include all available patients even if a patient has a missing value for one or more time points. However, missing data is likely, and we will plan to use multiple imputation (MI) to investigate the sensitivity of our results to missing data (36, 37).

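### The Aim 1-3 models adjust for no measure of other illness, although baseline medical history is collected, so general health may confound the two contrasts with surgery

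*Combined protocol and SAP*

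**What the plan says.** Under Primary Analysis for Aims 1-2, the covariates begin with "Key covariates that will be included in the aim 1-2 models are: time since injury at baseline" and continue with "physical limitations severity (mild, moderate severe"), "time on bladder management strategy recorded at baseline (<6 months, 6m-1.5 years, >1.5 years") and "age at baseline (coded as <20, 20-30, 30-40, 40-50, >50), sex, follow-up time point and BMI". The Analysis Plan Overview describes the comparison as made "with adjustment for demographic factors and injury characteristics".

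The other models take over this set:

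- The time-varying secondary analysis keeps the same covariates and drops one interaction.
- The subscale analyses repeat the primary model.
- The Aim 3 model adds cumulative complications and their interaction with treatment group.
- The exploratory step in the primary analysis adds only interactions between treatment group and covariates already listed.

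On data collection, the Procedures section (Baseline Visit) states: "The patient will be asked very routine questions about his/her health, medication usage, surgical history, physical exam findings". The same section lists, among the baseline data held in REDCap, "date of injury, previous medical history information, and current medical history information".

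**The concern.** Patients are not allocated to a method; they arrive already using or starting one. The third group consists of people who have had a diversion or augmentation operation. Whether someone has an operation commonly depends in part on other illness, and other illness plausibly lowers a score covering physical, mental and social function. A variable related to both group and outcome, and absent from the model, can produce a difference between methods that the methods did not cause, or hide one that they did.

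Two of the three pair-wise contrasts involve surgery. Each is tested at 0.017, and the Analysis Plan Overview gives counselling of patients on treatment options as the purpose. A contrast that partly reflects who was selected for an operation would serve that purpose poorly. A larger cohort does not help: the standard error shrinks and the bias does not.

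**Working it through.** **Check of the text.** Setting each model beside the baseline data gives:

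| Model | Adjustment terms | Term for other illness |
|---|---|---|
| Aims 1-2, primary | time since injury, limitation severity, time on method, age, sex, time point, BMI | none |
| Aims 1-2, time-varying treatment | same | none |
| Subscales | same | none |
| Aim 3 | same framework, plus complications and their interaction with treatment | none |

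No propensity method or sensitivity analysis for confounding is planned. The multiple imputation in A Note on Missing Data deals with missing values only.

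**Illustration of size.** The plan has no power calculation, SD or expected group sizes, so there is no figure of its own to reproduce. From the documents come the 0.017 level (sidedness not stated; two-sided assumed), five time points, and two cohort sizes: 1,500 in the background text and 4,200-4,400 under Study Population (midpoint 4,300). Everything else is assumed:

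- Serious non-urological illness differs by 10-20 percentage points between IDC and surgery and lowers the score by 0.5 single-visit SD.
- Within-patient correlation ρ is 0.6-0.7.
- Groups are equal, or split 50/30/20 with IDC 30% and surgery 20%.

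Step 1, bias = imbalance × effect: 0.10 × 0.5 = 0.05 SD and 0.20 × 0.5 = 0.10 SD. This ignores whatever age, BMI, limitation severity and the other covariates already absorb, so the residual range is taken as 0 to 0.10 SD.

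Step 2, variance of a mean of five scores = (1 + 4ρ)/5: 0.68 for ρ = 0.6 and 0.76 for ρ = 0.7.

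Step 3, standard error of IDC minus surgery with 1,500 patients:

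- Equal groups, ρ = 0.6: √[0.68 × (1/500 + 1/500)] = 0.0522.
- 450 against 300, ρ = 0.7: √[0.76 × (1/450 + 1/300)] = 0.0650.

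Step 4, smallest significant difference with z = 2.387: 2.387 × 0.0522 = 0.12 SD and 2.387 × 0.0650 = 0.16 SD.

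Step 5, chance of significance with no true difference = Φ(−2.387 + bias/SE) + Φ(−2.387 − bias/SE):

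| Residual bias | 1,500 patients | 4,300 patients |
|---|---|---|
| 0 | 1.7% | 1.7% |
| 0.05 SD | 5-8% | 14-22% |
| 0.10 SD | 20-32% | 59-81% |

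The formula is symmetric, so a bias in the other direction gives the same chances.

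**Cross-check.** A simulation of 1,000 runs with 500 per group took an SD of 1 for the patient average, a 0.5 SD effect and a 20-point imbalance. The estimated bias was 0.10 SD with 21% false positives when the health term was left out, and about 0.00 SD with 1.5% when it was included. That is a best case, because the health variable was measured without error and was not a consequence of the method.

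**The case against.** **Fitness selection is inferred.** A reader might infer that the surgical group contains only patients fit enough for an operation. No section describes how patients were selected for surgery or reports health by group. Fitness would also have been judged at the operation, and time on method extends beyond 1.5 years, so health at enrolment may differ. This stands: the text supports only a plausible difference.

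**Direction is unknown.** A reader might go on to infer that the contrasts will favour surgery. Selection could also depend on severity or on failure of another method, which could push the other way. This stands.

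**Size is assumed.** What matters is the imbalance left after the listed covariates. At a residual of zero the test keeps its 1.7%. This stands, and is why the range starts at zero.

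**The aim is associational.** The Analysis Plan Overview says that causal effects of full treatment histories cannot be evaluated. That limits the claim but does not remove the point, because the plan chooses to adjust, tests three contrasts and intends them for counselling.

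**The list may be open.** It is called a list of key covariates, which does not strictly close it. But no other main effect is named, and one added after scores are seen would be a post hoc choice.

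**Adjustment can mislead.** Patients enrol as existing users, so a condition recorded at baseline may have followed from the method. The Overview also says covariates before baseline are unavailable, and no section says onset dates are recorded. This stands, and argues against putting the term in the primary model.

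**The data may not be ready to use.** The documents mention routine health questions and medical history, not a structured list of conditions. This stands as a caution on cost.

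**Conclusion.** The omission holds: no Aim 1-3 model adjusts for other illness, while health and medical history are taken at baseline and stored. Because treatment is not randomised and one group is surgical, confounding of the CIC-surgery and IDC-surgery contrasts is plausible.

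The documents do not establish that it occurs, which way it runs or how large it is. The 1.7% to 20-32% range for IDC-surgery with 1,500 patients rests wholly on the assumed imbalance, effect, correlation and group split. No figure is offered for CIC-surgery. Nor do the documents support saying that the primary model is wrong for its stated descriptive target. What is missing is a check that readers will need before using the contrasts in counselling.

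**What to change.** Before any scores are analysed, pre-specify a count of non-urological chronic conditions from the baseline history (0, 1, 2 or more). Where dates allow, restrict it to conditions that predate the current method. Keep the current primary model. Beside it, as a planned sensitivity model, report the three pair-wise contrasts for Aims 1-2 and the Aim 3 interaction with and without this term.

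No new data collection is proposed: the cost is one derived variable and a short addition to the plan. There are three downsides. The list of qualifying conditions must be fixed in advance. The detail of the history may vary between the four sites and between clinic and telephone interviews. Conditions that arose after the method began may partly be its consequence, so a shift in the adjusted contrast could reflect removal of confounding or removal of part of the association itself, and the report should say so.

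### The primary model represents the injury only by time since injury and an undefined three-grade limitation rating; level, completeness and cause are in no model, so residual confounding by indication is likely.

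*Combined protocol and SAP*

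**What the plan says.** The Analysis Plan Overview says the association between method at enrolment and outcome will be estimated "with adjustment for demographic factors and injury characteristics". It does not itemise the injury characteristics.

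The section Primary Analysis for Aims 1-2 gives the covariate list. Two entries concern the injury or its consequences: "time since injury at baseline (coded as a categorical variable with levels <1 year, 1-5 years, and >5 years", and "physical limitations severity (mild, moderate severe". The others are time on the bladder method, age, "sex, follow-up time point and BMI".

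The same section then hypothesises that "interaction effects exist between treatment group at baseline and time on baseline treatment, time since injury, injury severity and patient age". Injury severity is not in the covariate list under that name and is not defined. It returns in Secondary and Additional Analyses for Aims 1-2, where the predictors of switching include "time on baseline treatment, time since injury, injury severity, patient age, sex and BMI".

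The subscale models repeat the primary model, the time-varying analysis keeps its key covariates, and Aim 3 uses a similar framework with complications added. None adds level, completeness or cause. The plan describes no propensity score, matching or sensitivity analysis for unmeasured confounding; its one stated sensitivity analysis concerns missing data.

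Under Study Procedures, the baseline interview covers history, examination findings and bladder specifics. The only injury item named among the stored baseline data is the date of injury. The summary and the Procedures text admit patients with spinal cord injury or neurogenic bladder, so not every participant need have a spinal cord injury.

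**The concern.** The three contrasts between methods are tested formally at 0.017, and covariate adjustment is the only protection they have against differences between the groups. Neurological level and completeness help to determine what a patient can do, and so plausibly which method is used. They also plausibly affect physical and social quality of life directly. For a patient without spinal cord injury, the cause of the neurogenic bladder may play the same part.

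A three-grade rating with undefined boundaries is at best a proxy for these factors. Whatever it fails to capture stays in the contrast and may be read as a difference between methods. A larger sample does not reduce this bias; it only makes a given bias more likely to reach significance.

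There is also a plain specification gap. Injury severity is a named interaction term and a named predictor of switching, yet an analyst has to guess which variable it is.

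**Working it through.** **Comparing the text.** The plan states no figure that tests this point, so the first check is of the wording.

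1. The overview commits to unspecified injury characteristics. The covariate list supplies time since injury and the limitation grade, and nothing on level, completeness or cause.
2. Injury severity occurs three times in Primary Analysis for Aims 1-2 and once in the switching model. In the switching list it stands among the same companions as the limitation grade does in the covariate list. The plan's profile count of 3^5 = 243 treats it as a three-level factor. It is therefore probably the limitation grade, but this is inference. The count is weak evidence, because it also treats age as three-level although age is coded in five.

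**Illustration of size.** The documents give no SD, effect size, group sizes or distribution of injury level by method. Inputs from the documents: five time points; 0.017 per contrast (0.05/3 = 0.0167), taken as two-sided, so z = 2.387; 1,500 patients in the summary; 4,400 as the upper end of the all-centres range under Study Population. Assumed inputs: equal thirds, within-patient correlation 0.6, and the two bias inputs below.

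Bias = (difference between two methods in the share with the omitted factor, after adjustment) x (effect of that factor on the score in SD, given the other covariates):

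- Low: 0.10 x 0.3 = 0.03 SD
- Central: 0.20 x 0.5 = 0.10 SD
- High: 0.30 x 0.8 = 0.24 SD

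Standard error of a contrast of five-score averages = sqrt(((1 + 4 x 0.6)/5) x 2/(N/3)), where (1 + 2.4)/5 = 0.68. The smallest significant difference is 2.387 times this:

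- N = 1,500: sqrt(0.68 x 2/500) = 0.0522; x 2.387 = 0.124 SD
- N = 4,400: sqrt(0.68 x 2/1,466.7) = 0.0305; x 2.387 = 0.073 SD

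With no true difference, the chance of p < 0.017 is Φ(bias/SE - 2.387) + Φ(-bias/SE - 2.387):

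| Bias | N = 1,500 | N = 4,400 |
|---|---|---|
| 0.03 SD | 4% | 8% |
| 0.10 SD | 32% | 82% |
| 0.24 SD | 99% | over 99% |

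The nominal value is 1.7%. At N = 1,500 the central bias lies below the smallest significant difference; at N = 4,400 it lies above it.

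**The case against.** The plan claims association and disclaims causal effects of full treatment histories. It adjusts for two injury-related terms, and a functional grade may remove much of the confounding by level and completeness. The illustration is assumed throughout. In particular, the 0.5 SD effect should be the effect given limitation grade and the other covariates, which is probably smaller than the unadjusted effect. Unequal groups would also raise the significance threshold.

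The points about the illustration stand, and they limit what can be said about size. The disclaimer helps only in part: it concerns treatment history before baseline, whereas the same overview speaks of counselling patients on treatment options and promises injury adjustment.

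A reader might also infer four stronger claims that the documents do not support:

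- **That the plan breaks its promise.** Time since injury is an injury characteristic and is in the model, and the overview never names level or completeness. The promise is met thinly, not broken.
- **That the limitation rating is taken after the method has been in use, so adjusting for it removes part of the difference of interest.** The time of rating is not stated, patients just starting a method are eligible, and nothing says the method causes limitation. The overlap with the Neuro-QoL physical domain ("subdomains of these surveys, which include physical, mental and social function for the Neuro-QoL") is not in itself a bias.
- **That level and completeness remain wholly confounded with method.** The documents give no distribution of either by method.
- **That these data are not collected.** The history and examination items could contain them, and the case report form is not among the documents.

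**Conclusion.** The point holds in a limited form. The primary model captures the injury only through time since injury and an undefined three-grade rating; level, completeness and cause are in no model; and injury severity is used without definition. These are facts of the text.

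That residual confounding by indication is likely is a judgement. It rests on non-random choice of method and on the plausible link of the injury to both method and quality of life. The size is unknown. The 0.10 SD figure (0.03 to 0.24) shows only that moderate assumptions give a bias comparable to the smallest difference the study would call significant, about 0.12 SD at 1,500 patients and 0.07 SD at 4,400. It is not evidence of a bias of that size here. The change should be made because the remedy is cheap and covariate adjustment is the only safeguard for the contrasts.

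**What to change.** 1. Confirm that the baseline interview captures neurological level, completeness of injury and cause of neurogenic bladder; add the fields if it does not.
2. Include all three as covariates in the Aim 1-3 models. Give participants without spinal cord injury their own category, so that none are dropped because level and completeness do not apply to them.
3. Define injury severity in these terms, both for the treatment interaction and for the switching model.
4. State how the limitation grade is rated, by whom and when. Report the pairwise contrasts with and without it as a sensitivity analysis.

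The cost is a few fields at most in an existing 30-minute interview, SAP wording and some further parameters. For example, level in four categories (cervical, thoracic, lumbar-sacral, no spinal cord injury) adds three main effects and 3 x 2 = 6 interaction terms with the three methods. A complete/incomplete indicator adds one and two. That makes 12 in all, before any finer split by cause. This is small against 1,500 or more patients, although some combinations with method may be sparse.
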